16.2 Pharmacokinetic Summaries

16.2.1 Pharmacokinetic Concentrations

Individual plasma concentrations for salbutamol before the first quantifiable concentration will be set to zero. If a single value below the lower limit of quantification (LLOQ) occurs between measurable concentrations in a profile, the LLOQ will be set to missing. If two or more LLOQ values occur in succession between measurable concentrations, the LLOQ will be set to zero, and the profile will be deemed to have terminated at the last measurable concentration prior to these LLOQs; for the purpose of individual plots, these non quantifiable results (NQ) will be set to 0 and the subsequent measurable concentrations will be retained. The LLOQ value which are after the last measurable concentration will be set to missing in the individual subject plots.

If there is physiological or operational plausibility for erratic absorption - NQ in the middle of a concentration profile may be set to missing while subsequent valid concentrations are retained.

Descriptive statistics (n, arithmetic mean, SD, CV, 95% CI of arithmetic mean, median, min, and max) will be used to summarize the plasma concentrations by treatment at each scheduled time point. In the calculation of descriptive statistics, all LLOQ values will be set to zero except when an individual LLOQ falls between two quantifiable values in which case it will be omitted (set to missing) from the calculation. Descriptive statistics at a time point where one or more samples have LLOQ values will be reported (as per listings), irrespective of the number of LLOQ results.

Participants excluded from the PK analysis set will be flagged in the listing and excluded from descriptive statistics.

All individual participant PK concentrations, time deviations and comments will be listed.

Linear and semi-logarithmic plots of the arithmetic mean plasma concentration by scheduled sampling time will be provided for each treatment (treatments in one plot). Linear plots will show the zero concentrations before the first measurable concentration. These plots will show nominal (scheduled) time in hours. The plots will match the summary table results.

Linear and semi-logarithmic plots of the median plasma concentration by scheduled sampling time will be provided for each treatment (treatments in one plot). Linear plots will show the zero concentrations before the first measurable concentration. These plots will show nominal (scheduled) time in hours. The plots will match the summary table results.

Linear and semi-logarithmic plots of the individual plasma concentration by actual sampling time will be provided by participant (two PK profiles per participant in one plot). These plots will show actual time in hours. Linear plots will show the zero concentrations before the first measurable concentration. Individual plots will match the individual PK concentration results (and imputations).

Linear and semi-logarithmic spaghetti plots of the (combined) individual plasma concentrations by actual sampling times will be provided by treatment. These plots will show actual time in hours. Spaghetti plots will match the individual PK concentration results (and imputations) for each participant.

16.2.2 Pharmacokinetic Parameters

PK parameters for salbutamol will be estimated using non-compartmental methods with WinNonlin® (WNL).

The plasma PK parameters will be estimated from the concentration-time profiles. In estimating the PK parameters, below LLOQ (BQL) values prior to the first quantifiable concentration will be set to zero. BQL values that occur after the first quantifiable point will be considered missing. Values that are embedded between BQLs, or quantifiable values occurring after two or more BQLs, will be set to missing at the discretion of the pharmacokineticist. LLOQ value which are after the last measurable concentration will be set to missing. Actual sampling times, rather than scheduled sample collection times, will be used in all computations involving sample collection times. If the actual sample collection time or dose time is missing, the scheduled time will be substituted in order to calculate the PK parameter.

Descriptive statistics (n, arithmetic mean, geometric mean, SD, CV, geoSD, geoCV%, 95% CI of geometric and arithmetic mean, median, min, and max) will be used to summarize the calculated PK parameters by treatment. For tmax only median, min, max and 95% CI will be presented.

Participants excluded from the PK analysis set will be flagged in the listing and excluded from descriptive statistics.

All individual participant PK parameters will be listed.

The points to be included in the λz range will be determined after inspection of the semi-log concentration-time profiles. At least 3 points will be required to be used, the Cmax data point will not be included. Parameters based on adjusted r2 equal or below 0.85 will be flagged but not excluded from descriptive statistics.

If AUCextra value is above 20%, it will be flagged but not excluded from descriptive statistics if the proportion of AUC extrapolated that exceed 20% does not exceed 20% of the values. If more than 20% of the values exceed 20% or if an individual value is >40% then this will be discussed with the Sponsor.

The individual values and geometric mean of salbutamol AUCs and Cmax will be presented graphically versus treatment with a line connecting the geometric means of the treatments.

16.2.2.1 Statistical Analyses

Analysis will be performed to compare the PK profile of salbutamol HFA-152a MDI and salbutamol HFA-134a MDI (currently marketed Ventolin product). Analysis will be performed on the natural logarithm of AUC(0-30), AUC(0-t), AUC(0-inf) and Cmax using a linear mixed model with the treatment and period (dosing day) as fixed effects and subjects as random effects. A one model will be used, grouped by parameter.

Point estimates and 90% CIs for treatment differences on the log scale derived from the model will be exponentiated to obtain estimates for geometric mean (GM) ratios and CIs on the original scale. The within-subject coefficients of variation (CVw) for AUC and Cmax will be calculated based on the loge-normal distribution. The within-subject coefficients of variation (CVw) for AUC and Cmax will be calculated based on the loge-normal distribution.

Model Checking & Diagnostics:

- Model assumptions will be checked before analysis.
- The underlying distributional assumptions involved in the statistical analyses will be assessed by visual inspection of residual plots. Normality will be examined by normal probability plots while homogeneity of variance will be assessed by plotting the residuals against the predicted values for the model.
- If the assumptions are seriously violated, then alternative data transformations will be explored. If no suitable transformation can be found, equivalent nonparametric analyses (ex. Wilcoxon signed-rank test) will be performed.

The following kernel code of SAS PROC MIXED will be used:

```
proc mixed;
  by parameter;
  class subject treatment period;
  model log(value)= treatment period / ddfm=kenwardroger cl;
  random subject type=un;
  lsmeans treatment period /alpha=0.1;
  /*estimates for treatment order Test1-Ref*/
  estimate "T vs R" treatment 1 -1 /alpha=0.1;
run;
```

SAS code might be updated depending on the data. An unstructured type of the covariance matrices R (accounting for the within subject variability) and G (accounting for the between subject variability) will be used. If this model fails to converge, alternative covariance structures may be considered based on a lower AIC values (for example variance component, etc.). For the described linear mixed model analyses, the Kenward and Roger method for approximating the denominator degrees of freedom and correcting for bias in the estimated variance-covariance of the fixed effects will be used. Statistical analysis model table will present N, n, least squares GM values and associated 90% CI, GM ratios and associated 90% confidence intervals and within-subject CV.

Intercurrent events and handling of missing data:

- Participant level missing PK concentration considered as missing at random, will not be imputed.
- The PK concentration will be affected by occurrence of the intercurrent event (Treatment discontinuation of the study) would be treated as missing at random from the occurrence of the intercurrent event until the end of the study and only reliable available data will be used in the primary analysis and summary descriptive.

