4.0 Changes from Previous Version of Approved SAP

This is the second version of the SAP. Changes from the first SAP version:

- Public disclosure tables have been added.
- Additional imputation rules for partial dates have been added for AEs.
- Sections of statistical analysis on PK and PD parameters have been changed slightly to allow for data driven model modifications. In addition, participants with parameter results for only one treatment will no longer be excluded from the statistical analyses.
- Descriptive statistics for routine urinalysis has been added.
- Headline summary PK TFLs as a separate deliverable and dry-run delivery have been removed.

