- Where the investigator is interested in the treatment effects in a hypothetical scenario where all participants have taken dose correctly as prescribed. The individual PK data affected by occurrence of the intercurrent event would be treated as missing from the occurrence of the intercurrent event until the end of the treatment (period) and consequently affected individual PK parameters will be missing for that treatment (period).

- **Rationale for estimand:** The test formulation is developed to have comparable PK characteristics and treatment effects. Interest lies in the PK values obtained while the participant is exposed to correct dose as prescribed, prior to the discontinuation of the randomized sequence and prior to the occurrence of emesis or coughing on dosing.
- **Population-level summary:** Ratio of geometric mean (for logarithmic transformed values) and 90% CI for the ratio of the geometric means for AUC(0-∞), AUC (0-t), AUC(0-30min), and Cmax.

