9.4.3 Hypothesis Testing

No formal hypothesis testing will be done.

No formal hypothesis will be tested. For each primary PK endpoint, point estimates and corresponding 90% CIs will be constructed for the ratio of the geometric mean of the test treatment to the geometric mean of the reference treatment, $\mu(\text{test})/\mu(\text{reference})$

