17.2.2.1 Statistical Analysis of Pharmacodynamic Parameters

Analysis will be performed to compare the PD parameters after dosing of salbutamol HFA-152a MDI and salbutamol HFA-134a MDI (currently marketed Ventolin product). Analysis will be performed on the natural logarithm of Emin and AUEC of serum potassium, and EMax and AUEC of heart rate and QTcF, using a linear mixed model with the treatment and period (dosing day) as fixed effects and subjects as random effects. A one model will be used, grouped by parameter.

Point estimates and 90% CIs for treatment differences on the log scale derived from the model will be exponentiated to obtain estimates for geometric mean (GM) ratios and CIs on the original scale. The within-subject coefficients of variation (CVw) for AUEC, Emin and Emax will be calculated based on the loge-normal distribution.

Model Checking & Diagnostics:

- Model assumptions will be checked before analysis.
- The underlying distributional assumptions involved in the statistical analyses will be assessed by visual inspection of residual plots. Normality will be examined by normal probability plots while homogeneity of variance will be assessed by plotting the residuals against the predicted values for the model.
- If the assumptions are seriously violated, then alternative data transformations will be explored. If no suitable transformation can be found, equivalent nonparametric analyses (ex. Wilcoxon signed-rank test) will be performed.

The following kernel code of SAS PROC MIXED will be used:

```
proc mixed;  
  by parameter;  
  class subject treatment period;  
  model log(value)= treatment period / ddfm=kenwardroger cl;  
  random subject /type=un;  
  lsmeans treatment period /alpha=0.1;  
  /*estimates for treatment order Test1-Ref*/  
  estimate "T vs R" treatment 1 -1 /alpha=0.1;  
run;
```

SAS code might be updated depending on the data. An unstructured type of the covariance matrices R (accounting for the within subject variability) and G (accounting for the between subject variability) will be used. If this model fails to converge, alternative covariance structures may be considered based on a lower AIC values (for example variance component, etc.). For the described linear mixed model analyses, the Kenward and Roger method for approximating the denominator degrees of freedom and correcting for bias in the estimated variance-covariance of the fixed effects will be used.

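### The SAP's model-failure fallback does not say that the log-scale geometric mean ratio with its 90% CI stays the primary result, so another analysis could replace it

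*SAP*

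**What the plan says.** SAP 5.3 sets the population-level summary for the four primary PK endpoints as the "Ratio of geometric mean (for logarithmic transformed values) and 90% CI for the ratio of the geometric means". SAP 9.4.3 says that for each of them "point estimates and corresponding 90% CIs will be constructed for the ratio of the geometric mean of the test treatment" relative to the reference, and also that "No formal hypothesis will be tested".

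SAP 16.2.2.1 obtains this from the natural log of each parameter with a "linear mixed model with the treatment and period (dosing day) as fixed effects and subjects as random effects", with intervals at the 90% level ("lsmeans treatment period /alpha=0.1"). Protocol 9.3.1 describes the same model. The results table is to show geometric mean ratios with 90% CIs.

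Under model checking, SAP 16.2.2.1 calls for a visual check of residual plots and gives no threshold. It continues, in words repeated in 17.2.2.1 for the PD parameters: "If the assumptions are seriously violated, then alternative data transformations will be explored". Then: "If no suitable transformation can be found, equivalent nonparametric analyses (ex. Wilcoxon signed-rank test) will be performed".

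Protocol 9.3.1 has no such fallback for PK, and SAP 7.1 does not list it among the changes from the protocol. SAP 6.2 releases the randomization code to the study team only after database lock.

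**The concern.** The fallback is an if/then rule, and nothing in either section says that the log-scale ratio and its interval survive once it is invoked. The natural reading is that the later analysis stands in for the earlier one. If one primary endpoint triggered it, that endpoint might be reported on another scale, or as a p-value, while the other three were reported as geometric mean ratios. The estimand would then go unanswered for that endpoint, and the four results would not be comparable.

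Three features make this worse:

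- The signed-rank test, the only method named, has no place for period, although the planned model contains it.
- No effect estimate or interval is specified for the fallback, although the study plans estimation and no testing.
- The trigger is a judgement on residuals from a model containing treatment. It is made once the code is available, so the primary analysis could change with the treatment results in view.

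**Working it through.** **1. The plan's own precision.** Inputs from SAP 6.1: within-participant CV 22% (AUC) and 25.4% (Cmax), n = 30, 24 or 18. For a two-period crossover on the log scale:

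half-width = exp( t(0.95, n−2) × σw × √(2/n) ) − 1, with σw = √ln(1 + CV²)

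- AUC: σw = √ln(1.0484) = 0.2174. At n = 30: exp(1.701 × 0.2174 × 0.2582) − 1 = 10.02%.
- Cmax: σw = √ln(1.0645) = 0.2500. At n = 30: exp(1.701 × 0.2500 × 0.2582) − 1 = 11.61%.

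| n | AUC, computed | AUC, SAP | Cmax, computed | Cmax, SAP |
|---|---|---|---|---|
| 30 | 10.02% | 10.02% | 11.61% | 11.61% |
| 24 | 11.38% | 11.38% | 13.20% | 13.20% |
| 18 | 13.49% | 13.49% | 15.66% | 15.66% |

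All six agree with n−2 degrees of freedom; n−1 gives 10.01% and 11.59% at n = 30. The stated precision therefore belongs to the log-scale analysis with period in the model.

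**2. What each analysis reports.**

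| Analysis | Geometric mean ratio | 90% CI for it | Period kept |
|---|---|---|---|
| Planned mixed model on logs | yes | yes | yes |
| Same model, non-log transformation | no | no | yes |
| Signed-rank test as named | no (p-value only) | no | no |
| Signed-rank plus Hodges-Lehmann interval on log differences (not specified) | ratio-type estimate | yes | no |

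**3. Width when period is ignored.** Let d be a participant's log test value minus log reference value, δ the log ratio and π the log period effect. Then d has mean δ − π in sequence AB and δ + π in BA, with variance 2σw² within a sequence. Pooled over 15:15, the mean is δ and the variance is 2σw² + π². The width should grow by a factor of roughly √(1 + π²/(2σw²)):

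- AUC, π = 0.2: √(1 + 0.04/0.0945) = 1.19.
- Cmax, π = 0.2: √(1 + 0.04/0.1250) = 1.15.

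Simulated AB/BA trials compared the signed-rank-based 90% interval on d with the Hodges-Lehmann interval from the between-sequence comparison of half period differences, which removes period. Extra width, log scale, 15:15:

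| Log period effect (assumed) | AUC, normal errors | Cmax, normal errors | AUC, t3 errors, same SD |
|---|---|---|---|
| 0 | none | none | none |
| 0.1 | 4% | 2% | 8% |
| 0.2 | 20% | 14% | 35% |
| 0.3 | 43% | 33% | 67% |

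**4. Bias when period is ignored.** The pooled mean of d is δ + π(n_BA − n_AB)/(n_AB + n_BA).

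- At 15:15 this is δ, so there is no bias.
- At 15:12 completers with π = 0.2 it is δ + 0.2 × (−3/27) = δ − 0.022. Simulation gives −0.02 to −0.025 on the log scale; the period-adjusted estimate stays at about δ.

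The documents give no dropout rate. SAP 6.1 says dropouts are not replaced, so some imbalance is possible.

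**The case against.** - **The ratio is promised without exception.** SAP 5.3 and 9.4.3 commit to it for every primary endpoint, and the model table lists it. A reader might infer that the SAP orders the ratio to be dropped; it does not say so. This stands: the defect is an unresolved ambiguity. But none of those passages says what happens under the fallback, so they do not settle it.
- **The signed-rank test is only an example.** A period-adjusted rank method with a Hodges-Lehmann interval on log data would also fit the wording. This stands, but it does not help the first step: another transformation already leaves the geometric mean ratio unestimated.
- **The period effects are assumed and large.** Log effects of 0.2 and 0.3 are exposure shifts of 22% and 35% between Day 1 and Day 4 (exp(0.2) = 1.22, exp(0.3) = 1.35). Confinement, dosing at the same clock time within an hour, standard meals and inhaler training before each dose all work against such shifts. This stands. At zero effect the cost is nil, and at 0.1 it is 2% to 4% with normal errors.
- **Normal data would never reach the fallback.** Fair, but with heavy-tailed t3 errors the penalty for AUC is larger.
- **Bias.** A reader might infer that the fallback gives a biased ratio in general. It does not: bias needs both a period effect and unequal sequences.
- **Complete pairs.** SAP 4.0 says "participants with parameter results for only one treatment will no longer be excluded from the statistical analyses", and a signed-rank test cannot use such participants. Nor can the rank method recommended here, so this does not separate the two.
- **CSR disclosure.** SAP 3.0 requires significant changes from the planned analysis to be identified in the CSR. A fallback that the SAP itself plans is not such a change.

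**Conclusion.** The point holds as a gap in the rule for reporting the primary result. Followed as written, SAP 16.2.2.1 and 17.2.2.1 can lead, after unblinding, to an analysis that gives no geometric mean ratio with 90% CI, and the signed-rank example also drops period. The documents do not support saying that the ratio will go unreported, that a signed-rank test is mandatory, or that the result is biased under the planned 15:15 allocation.

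The loss of the estimand follows from the wording and needs no assumption beyond the fallback being triggered. The precision penalty depends on period effects that the documents do not give. With normal errors it runs from nothing at zero to 43% extra width for AUC and 33% for Cmax at a log effect of 0.3. The bias of about −0.02 to −0.025 on the log scale needs an assumed period effect of 0.2 and three completers lost from one sequence only.

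Because the fallback is conditional, this is a cheap improvement and not a fault in the main analysis.

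**What to change.** In SAP 16.2.2.1 and 17.2.2.1:

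1. State that the log-scale mixed-model geometric mean ratio with 90% CI is always reported as the primary analysis (for PD, the main analysis), whatever the residual plots show.
2. State that any other transformation or nonparametric analysis is a sensitivity analysis only.
3. Replace the signed-rank example with the Hodges-Lehmann estimate and 90% CI from the between-sequence comparison of half period differences on the log scale, back-transformed to a ratio. With period 1 minus period 2, the half difference centres on (δ − π)/2 in AB and (−δ − π)/2 in BA. Their difference is δ, so period cancels.

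The cost is a few sentences and one short procedure; data collection is unaffected. The sponsor gives up the freedom to change the primary model after seeing the data. The sensitivity analysis uses only participants with both periods, as a signed-rank test would. Those with one period remain in the mixed model.

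### SAP 16.2.2.1 and 17.2.2.1: unstructured R plus G has one covariance parameter too many for a two-period crossover, the printed code fits a different model, and the variance behind the reported within-subject CV is not defined

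*SAP*

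**What the plan says.** The design (SAP 6.0) is two sequences, AB and BA, with 15 participants each and two periods. Neither treatment is repeated within a participant.

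For the log-transformed PK parameters, SAP 16.2.2.1 takes treatment and period as fixed effects and subject as random. It then sets the covariance structure: "An unstructured type of the covariance matrices R (accounting for the within subject variability) and G (accounting for the between subject variability". SAP 17.2.2.1 says the same for the PD parameters: "An unstructured type of the covariance matrices R (accounting for the within subject variability", again together with G.

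Both sections also print code, introduced by "The following kernel code of SAS PROC MIXED will be used". The RANDOM line is "random subject type=un" for PK and "random subject /type=un" for PD. Neither block has a REPEATED statement or a SUBJECT= option.

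The SAP leaves some latitude: "SAS code might be updated depending on the data". It adds "If this model fails to converge, alternative covariance structures may be considered based on a lower AIC values", with variance components as an example.

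The results table is to show "GM ratios and associated 90% confidence intervals and within-subject CV". The CV is to follow from the lognormal distribution, but no variance component is named as its input.

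Protocol 9.3.1 (PK) and 9.3.3 (PD) specify only period and treatment as fixed and participant as random. SAP 7.1, which lists changes from the protocol, mentions no change of covariance structure.

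**The concern.** With two values per participant, a full within-participant matrix already uses up all the covariance information. A participant variance on top of it cannot be separated from the common part of that matrix. The SAP describes R as the within-subject part, so an analyst could reasonably take the within-subject CV from R, which is the part the data do not pin down.

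The prose and the code also describe different models, and the SAP says of each that it will be used. Two programmers following the same document could fit different models and report different CVs. What is at stake is the reported CVw and the reproducibility of the specified model.

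**Working it through.** **1. The plan's own figures.** SAP 6.1 assumes CVw of 25.4% (Cmax) and 22% (AUC). With one within-participant variance w = ln(1 + CVw²), sqrt(w) is 0.2500 and 0.2174. The half-width is exp(t(0.95, n-2) × sqrt(2w/n)) - 1.

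| n | AUC: SAP / computed | Cmax: SAP / computed |
|---|---|---|
| 18 | 13.49% / 13.49% | 15.66% / 15.66% |
| 24 | 11.38% / 11.38% | 13.20% / 13.20% |
| 30 | 10.02% / 10.02% | 11.61% / 11.61% |

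All six figures reproduce, so the planning rests on a single residual variance.

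**2. Parameter count under the prose.** The covariance V of a participant's two log values has three distinct elements: V11, V12 and V22. Unstructured R has three parameters (r11, r12, r22) and the participant variance g adds one. Each element of V is the matching element of R plus g, so the map from four parameters to three elements has rank 3.

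**3. What is and is not identified.** Adding d to g and subtracting d from every element of R leaves V, and hence the likelihood, unchanged. The diagonal of R moves by d. Half the variance of the within-participant difference does not move: (r11 - d + r22 - d - 2(r12 - d))/2 = (r11 + r22 - 2 r12)/2.

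**4. Limits if CVw were read from the diagonal of R.** The documents give no between-participant CV. Assume 30%, so b = ln(1.09) = 0.0862. With V11 = V22 = w + b and V12 = b, the eigenvalues of R are w and w + 2b - 2g. R is non-negative definite for g from 0 to b + w/2, so its diagonal runs from w + b down to w/2.

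- Cmax: w = 0.0625. The diagonal runs from 0.0313 to 0.1487, a CV of 17.8% to 40.0%.
- AUC: w = 0.0473. The diagonal runs from 0.0236 to 0.1334, a CV of 15.5% to 37.8%.

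If the between-participant CV is taken as 20% to 50%, the lower limits stay put. The upper limits run from 32.7% to 57.5% (Cmax) and from 30.1% to 55.7% (AUC).

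**5. One simulated data set** (15/15, true CVw 22%, between-participant CV 30% assumed, R indexed by treatment):

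| g | -2 REML log-likelihood | GMR | SE (log scale) | CV from r11 / r22 | CV from half-difference |
|---|---|---|---|---|---|
| 0 | 48.758 | 1.0424 | 0.0609 | 38.1% / 41.8% | 23.9% |
| 0.03 | 48.758 | 1.0424 | 0.0609 | 33.4% / 37.4% | 23.9% |
| 0.06 | 48.758 | 1.0424 | 0.0609 | 28.0% / 32.6% | 23.9% |
| 0.09 | 48.758 | 1.0424 | 0.0609 | 21.6% / 27.2% | 23.9% |

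A random intercept with one residual variance gives GMR 1.0424, SE 0.0609 and CVw 23.9% on the same data. The SAP does not say whether R is indexed by treatment or by period. Indexing by period gave GMR 1.0454, a ratio of 1.0454/1.0424 = 1.003.

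**6. The printed code.** Without a REPEATED statement, R is sigma² times the identity, not unstructured. In the PD line, TYPE=UN without SUBJECT= read literally asks for an unstructured G over 30 participant levels: 30 × 31/2 = 465 parameters for 30 × 2 = 60 values. The PK line has no slash, so TYPE=UN there is not valid as an option. The mismatch with the prose does not depend on the slash.

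**7. Incomplete participants.** SAP 4.0 now keeps participants with only one treatment. In 200 simulated trials per setting (CVw 25.4%; between-participant CV 30% and 50% assumed), the GMR under UN by treatment was compared with the random-intercept GMR. With complete data the shift was 0.00%. With one to three participants assumed to lack period 2, median shifts were 0.04% to 0.10% and 95th percentiles 0.2% to 0.8%.

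**The case against.** The best defence is that the intended model can be read from everything else. The fixed and random effects in both SAP sections, protocol 9.3.1 and 9.3.3, and the sample-size figures all point to a participant intercept with one residual variance. The SAP calls its code a kernel, allows updates and names variance components as a fallback. CVw is not an endpoint or part of any estimand's population-level summary, and SAP 9.4.3 states that no formal hypothesis is tested.

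Most of this stands, and it is why the severity is minor. It does not remove the error. SAP 3.0 says the SAP supersedes the protocol's statistical considerations, so the covariance sentence governs. The fallback applies only on non-convergence, which a flat likelihood need not trigger; PROC MIXED itself was not run to see.

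A reader might go further and infer that the within-subject CV cannot be estimated at all. The documents do not support that. Only the diagonal of R is undetermined, the half-difference variance is unique, and the SAP never says CVw is taken from the diagonal of R.

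**Conclusion.** Wrong as written, minor severity. The covariance sentence in both sections specifies four parameters where three can be estimated, the printed code specifies a different model, and the input to the promised CVw is undefined.

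The ranges 17.8% to 40.0% and 15.5% to 37.8% apply only if CVw is read from the diagonal of R. They rest on an assumed between-participant CV of 30% and are theoretical limits at equal likelihood. They do not forecast what an analyst would report.

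A reader might also infer that the primary comparison is compromised. The documents do not support that. Under the prose model the GMR depends only on the marginal covariance. With complete data it matches the random-intercept result if R is indexed by treatment, and the simulated shifts with a few incomplete participants were well under 1%. One limit remains: the SAP prescribes Kenward-Roger intervals, and these were not computed, so the claim covers the ratio and its model-based standard error only.

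**What to change.** In SAP 16.2.2.1 and 17.2.2.1:

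- Replace the sentence on unstructured R and G with one random participant intercept and one residual variance. This is the model implied by protocol 9.3.1 and by the SAP 6.1 half-widths.
- Change both RANDOM lines to `random subject;`.
- Define CVw = sqrt(exp(residual variance) - 1).

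The cost is SAP wording and two code lines, with no change to data collection. The downside is that a common within-participant variance is assumed for both products. Tightening the AIC fallback, for example by naming one ordered alternative, is optional and not needed for identifiability.
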